In preterm infants, multiple-strain probiotics have proved more efficient in reducing NEC, sepsis and mortality than single-strain products (Chang 2017).

In a recent study from India, more than 4500 infants were randomized to receive either the probiotic bacteria *Lactobacillus plantarum* along with fructo-oligosaccharide, a plant-derived prebiotic (the combination of probiotic and prebiotic is coined “synbiotic”) or placebo (Panigrahi 2017). The synbiotic treatment was started on day 2-4 of life and was given for 7 days. This simple intervention reduced the composite outcome severe infections and/or death

[figure not shown]

Fig. 1. Prevalence of ESBL carriage in different age groups. The graph shows the prevalence (%) of ESBL carriage among the participants when categorized into five different age groups.

ProRIDE Trial in Tanzania

by 40%, from 9.0% in the placebo group to 5.4% in the synbiotic group (Fig. 2). This study has caused great attention in the scientific community and in the general public. Panigrahi has suggested that more studies are needed in order to develop guidelines for clinical care (The Wire 2017).

[figure not shown]

Fig. 2. Morbidity and mortality in infants given synbiotic versus placebo. Panigrahi, Nature 2017

A stable and resilient commensal gut microbiota is essential for “colonization resistance”; the ability to prevent intestinal colonization and invasion by pathogens. Resurrecting the gut microbiota by the use of probiotics has recently been put forward as a potential new strategy in combatting intestinal carriage of multi-drug-resistant (MDR) bacteria (Pamer 2016). To what extent probiotics directly reduce the spread of AMR is still much under investigation (Arthur 2016). However, probiotic bacteria can produce bacteriocins that improve mucosal integrity and thereby reduces the pathogenic bacterial population and promote “colonization resistance” (Pamer 2016), but there is so far no data on which probiotic strains that most effectively may reduce AMR in children. In adults and older children lactobacilli are often used to prevent or treat other conditions like antibiotic-associated diarrhea, gastroenteritis and infantile colic (Agamennone 2018 & Gutiérrez-Castrellón 2017). However, in breastfed infants, bifidobacteria constitute more than 80% of the gut microbiota (Fig. 3) and has several beneficial effects that make them attractive as probiotic agents for this age group.

ProRIDE Trial in Tanzania

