3.11.2 Laboratory tests which to be performed at UiB/SUH/UNN

Fecal samples and fecal swabs collected at six weeks and six months will be transported to Norway for the following analyses:

- Fecal swab samples (n=4000) collected at six weeks and six months will be screened for ESBL-E using a selective ESBL-screening agar (ChromID ESBL and ChromID Carba,

ProRIDE Trial in Tanzania

BioMerieux). All samples will be plated on non-selective plates for growth control.

ESBL-E isolates will be frozen for subsequent genetic analysis (whole genome sequencing and plasmid analysis).

- Fecal samples (n=4000) collected at six weeks and six months will be subjected to gut microbiota/metabolome and antibiotic resistome analysis using state of the art methods. . This will be done on DNA or metabolites extracted from the feces sampled and stored in a commercially available sampling kit (OMNIgen GUT/MET kits). In addition, fecal samples collected at six months will be analyzed to determine the levels of gut inflammatory markers between the two groups.

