Participants have been randomized to probiotic or placebo using fixed equal allocation ratios. An independent researcher/statistician at University of Bergen created a computer-generated randomization list, with the study identification number of patients, from 1 to 2000, allocated to probiotic or placebo. We have not planned for any restrictions to reduce the predictability of the randomization list. The probiotic and placebo are identical in taste and color, and produced in identical bottles. A pharmacist, who was not part of the study, was provided with the randomization list and labelled the identical bottles, numbered from 1 to 2000. This was performed before shipment to the study site. At the time of inclusion of infants in the ProRIDE study, study personnel provided the parents with consecutive, prelabelled bottles with probiotic or placebo according to the randomization list.

11. Sample size

Infant mortality rate in Tanzania was in 2018 reported at 3.8%. We do not have exact data for the Mbulu district, but we assume a similar rate of approximately 4%. Serious infections leading to hospitalization are probably equally common, but hospitalization rates may depend on available access. In the Panigrahi study, a synbiotic product was given for only seven days, and it reduced the composite outcome death and/or infection from 9.0% to 5.4% during the first two months of life. In our study, the intervention will continue for around four weeks and follow-up will continue until six months of life. We consider a similar reduction in the composite outcome death and infections leading to hospitalizations from 9.0% to 5.4%, as in the Panigrahi study, to be clinically relevant (1). To find this difference with a study power of 85% at 5% significance level a sample size of minimum 924 cases in each arm; thus 1848 infants is needed. In order to allow for drop-out we aimed to include 2000 infants. With this number of infants, we will also have sufficient power to detect a minimum of 30% reduction in ESBL-E colonization rate (from around 50% to 35%) at six months of age.

We finished recruitment of 2000 participants in January 2023 and will complete 6 months follow-up for all participants in July 2023.

12. Framework

The study will test the hypothesis of superiority of probiotic over placebo in preventing death or hospitalization during the first 6 months of life. Comparison of the proportion of participants with the primary outcome will be presented.

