13. Statistical interim analysis and stopping guidance

Interim analyses have been performed after six month follow-up of 500 and 1000 infants. The major outcomes and adverse outcomes of interest; mortality, hospitalizations and blood culture confirmed sepsis have been summarized and presented to the DSMB. Only the study statistician have had access to these results. If mortality between groups (probiotic vs placebo) at 6 weeks follow-up had been significantly different at the level of $p<0.05$ by Chi square test at assessment at these two time points of the study, the study would have been stopped. This decision had in that case to be taken by the PI of the study, in consultation with co-investigators and the DSMB. Other triggers that would call for an unscheduled DSMB review were if infant mortality or morbidity rates clearly exceed expected rates in Tanzania. Severe adverse events have also been reported consecutively to the DSMB, and the DSMB have evaluated this independently of the interim analysis.

14. Timing of final analysis

Final analysis of data will be performed after all patients have completed 6 months follow-up. This analysis will be performed on anonymized data. Blinding for investigators and patients will be maintained until the study is completed.

15. Timing of outcome assessments

The primary outcomes will be assessed at 6 months. Secondary outcomes will be assessed at 6 weeks and 6 months. Additionally, adverse events have been and will be reported to the DSMB consecutively for independent evaluation until the study is completed.

Statistical principles

16. Levels of significance, P values

Analysis results for the primary outcome will be reported as odds ratio with 95% confidence interval with P-value. The standard cut-off of $p<0.05$ will be used for statistical significance levels. For secondary outcomes we will report appropriate effects measures with 95% confidence intervals without p-values.

17. Rationale for any adjustment for multiplicity, and, if so how the type 1 error is to be controlled

Type I error will be controlled at the traditional 0.05 two-sided level for the hypothesis test. We will perform a hypothesis test only for the primary outcome and we will not need to adjust for multiple tests.

18. Confidence intervals to be reported

Odds ratios and other relevant effect-measures will be estimated in appropriate regression models and will be reported with 95% confidence intervals.

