In univariate analysis, comparison of proportions will be done using Pearson's chi-squared test and comparison of means will be done using t-test or non-parametric tests as appropriate. Logistic regression will be used for multivariate analysis when assessing the relative importance of risk factors for carriage of ESBL-E and other multi-resistant bacteria.

Stool microbiota, stool metabolome and stool inflammatory markers

Stool microbiota: A Poisson generalized linear model will be used to calculate trends in the relative abundance of genera and antibiotic resistance genes in the stool microbiota. Corrections based on multiple comparisons will be performed by the Benjamini-Hochberg false discovery rate (FDR). An FDR Q value $\leq .10$ will be considered significant for any analyses with multiple comparisons. A standard P value $\leq .05$ will be considered significant for all other analyses. Alpha diversity of the gut microbiota will be assessed by calculating the Shannon Diversity index (MEGAN, v5.10.6). Multiple beta diversity metrics of

samples will be performed by using non-metrical multidimensional scaling (NMDS), based on a matrix of Bray-Curtis distances and calculated by using the vegan R package. Differences between groups will be tested by using permutational multivariate analysis on beta diversity matrices.

Stool metabolites will be identified by using mass spectral (MS) databases (e.g., MzCloud, Metlin) and standards purchased for this project. For statistical and pathway analyses, we will use web-based tool MetaboAnalyst. All MS data will be submitted to and stored at the European Bioinformatics Institute repository MetaboLights. Stool inflammatory markers will be analysed with conventional statistical tools for interval data using parametric or non-parametric tests, as appropriate.

28. Missing data

Missing data for both binary and continuous variables will in the main analyses be handled as non-responses. Depending on the degree of missingness, we will perform supplementary analyses with multiple imputation of missing values to assess the possibility that the missing data may introduce bias.

29. Statistical software

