Statistical analysis will be performed in R version 4.2.2 or higher (The R Foundation for Statistical Computing, Vienna, Austria). Mixed effects models analysis in R will be performed using the “lme4” or “lmerTest” packages. If imputation is considered necessary or useful, regression analysis with multiple imputation will be performed, and imputation will be done using the mice.impute.bygroup function in the “mice” and “miceadd” libraries in R.

Publication plan

30. Primary outcome

The first main paper will present the effect of probiotic administration on the primary outcomes (death and/or hospitalization) and the following secondary outcomes: carriage of ESBL-producing Enterobacteriales and the taxonomy of the gut microbiota in the two study arms. Safety of the probiotics will be described in the same paper, with focus on adverse events.

31. Secondary outcomes

Further analysis of the effect of the probiotics on prespecified secondary outcomes will be published separately.

32. Cost-efficacy and ethical issues

Given a positive effect of probiotics, cost-benefit considerations of probiotic treatment will be published focusing on the perspectives of the individual patient and society at large, including data on hospitalization, healthcare use, etc.

References

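### SAP 27 fits a Poisson model to relative abundance with no unit, offset or variance correction, so per-genus and per-gene intervals and Q-values are generally wrong

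*SAP*

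**What the plan says.** The stool microbiota part of SAP 27 says: "A Poisson generalized linear model will be used to calculate trends in the relative abundance of genera and antibiotic resistance genes". Benjamini-Hochberg correction follows, and a Q value of .10 or less "will be considered significant for any analyses with multiple comparisons". Overall composition has its own test: "Differences between groups will be tested by using permutational multivariate analysis on beta diversity matrices".

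Neither document says whether the response is a fraction, a percentage, reads per million or a raw count. Neither gives an offset for read depth, a dispersion parameter or a robust variance. SAP 29 says "Mixed effects models analysis in R will be performed using the" lme4 or lmerTest packages, without linking them to the stool data. Protocol 7.0 contains no microbiota model.

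Microbiota and resistome at six weeks and six months are secondary outcomes (SAP 26). SAP 16 commits to intervals for such outcomes: "For secondary outcomes we will report appropriate effects measures with 95% confidence intervals without p-values". Gut taxonomy in the two arms is planned for the first main paper (SAP 30), and Protocol 13.0 lists a microbiota and resistome paper. On volume, Protocol 3.11.2 says: "Fecal samples (n=4000) collected at six weeks and six months will be subjected to gut microbiota/metabolome and antibiotic resistome analysis".

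**The concern.** A Poisson model fixes the variance equal to the mean. That is a statement about counts of independent events. A relative abundance is not such a count, and read counts from different infants vary far more than Poisson sampling allows. The fitted ratio is still a sensible estimate, but its standard error comes from an assumption that the data need not meet.

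The error can go in either direction. On one scale real differences in uncommon genera are hidden; on another nearly every genus is declared different. Benjamini-Hochberg takes the p-values as given and cannot repair them. Which genera and resistance genes are reported can thus turn on a data-entry choice that the plan does not make.

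**Working it through.** **The plan's own figures.** The documents give no figure for this model. The primary sample size (9.0% versus 5.4%, 85% power, two-sided 5%) reproduces: 925 per arm with pooled variance against 924 stated, and 85.0% power at 924. Nothing below affects it.

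**Inputs.** Protocol 3.11.2 plans 4000 samples over two visits, so 2000 per visit and at most 1000 per arm. I assume n = 900 per arm. Abundances, coefficients of variation between infants (CV), mean counts and dispersions are also assumptions, because the documents give none.

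**1. Dependence on the unit.** This step is algebra. Let the response be c times the fraction, with arm means m0 and m1 as fractions. For a two-arm log-link Poisson fit:

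- log ratio = log(m1/m0), free of c
- SE = sqrt(1/(c·n·m0) + 1/(c·n·m1)), proportional to 1/sqrt(c)

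For m0 = 0.02 and m1 = 0.022, log(1.10) = 0.0953. As fractions the arm sums are 18 and 19.8, so SE = sqrt(1/18 + 1/19.8) = 0.326.

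| Unit | SE | z | 95% CI of ratio |
|---|---|---|---|
| fraction | 0.326 | 0.29 | 0.58–2.08 |
| percent | 0.0326 | 2.93 | 1.03–1.17 |
| per million | 0.00033 | 293 | 1.099–1.101 |

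The choice of n does not matter to the argument. With 500 per arm each z is multiplied by sqrt(500/900) = 0.745, giving 0.22, 2.18 and 218. A direct fit to one simulated data set (1000 per arm) on scales 1 and 100 gave the same estimate, model SEs of 0.2011 and 0.0201, and a sandwich SE of 0.0585 on both.

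**2. False positives on proportions.** The true SE is about CV·sqrt(2/n), so a nominal 5% test rejects a true null with probability 2Φ(−1.96/(CV·sqrt(mean in the chosen unit))), whatever n is. At 2% abundance and CV 0.5 to 3 this gives 0% as fraction, 0.6–64% as percent and 98–99.6% per million.

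**3. Lost power on the fraction scale.** Detection probability = Φ((log 1.25 − 1.96·SE)/(CV·sqrt(2/n))) for a true ratio of 1.25 and CV 0.5 to 1.5. It is 0% at 2% abundance, 0–1% at 5%, 1–22% at 10% and 65–88% at 20%. With a variance estimated from the data it would be 88–100%.

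**4. Read counts.** At equal depth, null rejection = 2Φ(−1.96/sqrt(1 + mean × dispersion)).

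| Mean count | Dispersion 0.1 | Dispersion 1.0 |
|---|---|---|
| 1 | 6% | 17% |
| 5 | 11% | 42% |
| 100 | 55% | 85% |

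It stays below 10% only if mean × dispersion is under about 0.42. An offset does not cure this: in simulated counts at depth about one million with a log-depth offset, plain Poisson rejected 98–99.8% of true nulls and sandwich variance 5–6%.

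**5. Effect on the Q-values.** With 100 features, none truly different (mean abundance 5%, intraclass correlation 0.1, 1000 per arm), Q ≤ .10 declared on average 0 features as fraction, 53 as percent and 99.6 per million.

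**6. Is sandwich variance enough?** Not for every feature. In simulation with 50–79% zeros, strong skew (log SD 2) and 20 of 100 features truly different, the false share at Q ≤ .10 was about 19–40%. P-values from re-allocated arm labels, using the robust z, rejected 4–5% of true nulls at 80–95% zeros. That check used 499 re-allocations at the 5% level. With 499, the smallest possible p is 1/500 = 0.002, above the first Benjamini-Hochberg threshold for 100 features, 0.10/100 = 0.001.

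**The case against.** **The plan does not say that this model compares arms.** SAP 27 speaks of trends and assigns group differences to the permutation test. With two visits, a trend could mean change over time. This stands. The arm comparison is inferred from Protocol 2.2.6, which compares microbiota between the groups, and from SAP 30. The standard-error problem applies to either contrast.

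**The analyst may add a variance correction.** A mixed Poisson model in lme4 is one way to allow extra variation, and quasi-Poisson is another. The plan commits to neither. Quasi-Poisson also fails when read depth varies: null rejection was 17–23% at a depth log SD of 1.0. What SAP 27 does name is a Poisson model, and followed as written it gives wrong standard errors, so this is more than missing detail.

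**The sizes rest on assumptions.** This stands for steps 2 to 6. A reader might infer that most declared genera would be false. The documents do not support that, because they give no read depth, mean count, dispersion or number of truly different features. For rare features entered as counts the test is close to nominal.

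**The outcome is secondary.** True, and the overall permutation test is sound, but it gives no result for a single genus or gene.

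**Conclusion.** The point holds. As written, the per-feature standard errors, intervals and Q-values in SAP 27 are generally wrong. Their dependence on the unit is algebraic and needs no assumption; the size of the error depends on the assumed abundances, dispersions and counts. A unit can be right by chance for one feature, but no single unit is right for all.

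Three stronger readings are not supported:

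- That the model always gives false positives. On the fraction scale it is conservative, and abundant genera can still be detected; Protocol 1.1 says that "in breastfed infants, bifidobacteria constitute more than 80% of the gut microbiota".
- That the microbiota results as a whole fail. The abundance ratios and the overall permutation test are unaffected.
- That the trial's main conclusion is at risk. The primary outcome test and the sample size are untouched.

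How SAP 16 and 17 fit with the p-value rules in SAP 27 is a separate question and adds no weight here. The change should be made because taxonomy by arm is planned for the first main paper.

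**What to change.** Amend SAP 27 before stool data are linked to arm:

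- State the contrast: probiotic versus placebo, separately at six weeks and six months. If a time trend is also wanted, account for repeated samples from the same infant.
- Fit a log-link model to read counts per genus or gene, with log total reads as offset, and report sandwich 95% intervals.
- Take the p-value for every feature from random re-allocation of arm labels, using the robust z statistic. SAP 10 supports this: "We have not planned for any restrictions to reduce the predictability of the randomization list", which I read as no blocking or stratification.
- Define the Benjamini-Hochberg family (which visits, genera and genes it covers) and use enough re-allocations for its smallest threshold. For 100 features at Q ≤ .10, at least 10,000 would do, since 1/10,001 is about 0.0001 against the threshold of 0.001. A larger family needs more.

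The cost is SAP wording, a changed model call, more computing time and wider intervals than a plain Poisson count model gives. No new data are needed.

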3.8.5 Visit schedule and follow-up activities

The follow-up schedule is summarized in Table 1 below. After study randomization, participants will receive follow-up for six months. At enrollment the baby will be weighed and clinical data on mother and child will be entered in the CRF. The first visit after enrolment will be around 7 days after birth, the second at six weeks after initiation of intervention product, and the last visit at six months. During all study visits, the baby's length, weight measurements, and clinical information will be recorded. Fecal samples and fecal swabs will also be taken according to the developed SOP.

Table 1. Follow-up schedule visit for ProRIDE-trial

| Time | Event | Activity |
|----------------------------------------------------------------------|-----------------------------|-------------------------------------------------------------------------------------------------------------------------------------------------------|
| Day 0-3 after birth of the newborn | Enrolment and randomization | - Filling of CRF-1 - Giving the IP/placebo to the mother/caretaker of the baby |
| Day 7 after initiation of investigational product | Visit 1 | - Observe for the compliance - Discuss issues with care takers |
| Six weeks after initiation of investigational product | Visit 2 | -Observe if the bottle with IP/placebo is empty and return the bottle -First fecal and fecal swab sample will be taken -Filling of CRF-2 |
| Six months (25-27 weeks) after initiation of investigational product | Visit 3 | -Second fecal and fecal swab will be taken - Filling of CRF-3 |

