Patients will be recruited among newborns; born at Haydom Lutheran Hospital (HLH) in North East Tanzania and out-born newborns in the surrounding area. HLH is located in the Mbulu district, at the western end of the Manyara region in the North-Central Tanzania, about 300 km south-west from regional center Arusha. The HLH catchment area consists of four administrative divisions, three districts and two regions. These are the Dongobesh and Haydom divisions in Mbulu District, the Basotu Division in Hanang District (Manyara Region), and the Nduguti Division in Iramba District (Singida Region). The hospital serves a population of more than two million people from five regions. Annually, there are more around 3900 deliveries in the hospital, and in 2018 the neonatal mortality rate in Tanzania was around 21/1000 live births.

24. Withdrawal / follow-up

Participation is based on informed voluntary consent of the parents of the child. Parents may decide that their child may withdraw at any time of the study without giving reasons or justification. Upon withdrawal, no further data will be collected. However, data recorded up until the time of withdrawal will be included in the analysis.

25. Baseline patient characteristics

Baseline data on demographic characteristics are recorded as detailed in the eCRF.

Analysis

26. Outcome definitions

Primary outcome

Prevalence (%) of the composite outcome death and/or hospitalizations at six months of age.

Secondary outcomes

- Rates (%) of ESBL-E colonization at six weeks and six months of age.
- Rates (%) of hospitalizations up to six months of age.
- Rates (%) of confirmed sepsis (blood culture-confirmed) episodes up to six months of age.
- Growth monitored by length and weight up to six months of age.
- Stool microbiota composition including resistome analysis (metagenome sequencing) at six weeks and six months of age.
- Stool metabolome composition at six weeks and six months of age.
- Stool inflammatory markers at six months of age
- Genetic characteristics of ESBL-E from colonization and clinical samples (targeted screening).
- Risk factors for death, hospitalization and sepsis.
- Primary and secondary outcomes will secondarily be performed stratified for place of delivery, ie hospital, home or primary health care facility.

27. Analysis methods

Clinical and microbiological data

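### SAP section 27 does not say how an infant's two stool samples enter the microbiota tests, and a plain Poisson variance does not suit relative abundances even at one visit

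*SAP*

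**What the plan says.** Protocol section 3.8.5, Table 1, schedules stool at two visits: at six weeks "First fecal and fecal swab sample will be taken", and at six months "Second fecal and fecal swab will be taken". Protocol section 3.11.2 gives the laboratory load: "Fecal samples (n=4000) collected at six weeks and six months will be subjected to gut microbiota/metabolome and antibiotic resistome analysis". With 2000 infants, that is two samples each.

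SAP section 26 lists the outcome as "Stool microbiota composition including resistome analysis (metagenome sequencing) at six weeks and six months of age", and SAP section 15 says "Secondary outcomes will be assessed at 6 weeks and 6 months".

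SAP section 27 describes the ordination as "based on a matrix of Bray-Curtis distances and calculated by using the vegan R package". On the comparison of arms it says "Differences between groups will be tested by using permutational multivariate analysis on beta diversity matrices". For genera and resistance genes it names a Poisson generalized linear model to estimate trends in relative abundance. It mentions no visit term, infant identifier, unit of permutation, clustered variance or over-dispersion.

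SAP section 29 says "Mixed effects models analysis in R will be performed using the" lme4 or lmerTest packages, without naming an outcome.

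**The concern.** Arm was assigned to infants, so the infant is the unit that a permutation test of arm must shuffle. An infant's two stools share an arm and usually resemble each other. If both visits go into one distance matrix and the samples are shuffled singly, the reference distribution breaks that pairing and no longer matches the randomization.

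The abundance model has a related problem. With two sampling times, a trend is most naturally read as change between visits, which puts both samples of an infant in one model. A model that ignores the pairing gives a standard error that is too small for the average arm effect and too large for the change and arm-by-visit terms.

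The gap matters because SAP section 30 puts gut microbiota taxonomy by arm in the first main paper. The same sentence in section 27 can also be carried out as a valid test, a liberal one or a conservative one. Nothing in the SAP stops that choice being made after the data are seen.

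**Working it through.** **Inputs.** Two samples per infant, 1:1 allocation and a nominal 5% level come from the documents. The documents give no within-infant correlation, no size of age shift, no over-dispersion and no error rate for the microbiota analyses. There is thus no planned figure to reproduce, and the values of *r* (within-infant correlation), shift and dispersion below are assumptions.

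**1. Pooled visits, samples shuffled freely, no age shift.** The variance of the arm contrast is (1 + *r*) times what the shuffle assumes. For *k* equal effective dimensions with 5% critical value *c*, the true level is P(χ²ₖ > *c*/(1 + *r*)). At *r* = 0.3:
- *k* = 1: 3.841/1.3 = 2.955, giving 0.086
- *k* = 5: 11.07/1.3 = 8.516, giving 0.130

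The table sets this beside a simulated Bray-Curtis permutation test with no true arm effect (60 infants × 2 samples, 40 genera, 500 runs, 299 permutations). The last two columns span three sizes of age shift, including none.

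| *r* | Formula, *k* = 1 / 5 / 10 | Free shuffle, no shift | Shuffle within visit, infant ignored | Whole infants shuffled |
|---|---|---|---|---|
| 0.1 | 0.062 / 0.073 / 0.083 | 0.074 | 0.068-0.082 | 0.052-0.062 |
| 0.2 | 0.074 / 0.100 / 0.123 | 0.112 | 0.060-0.108 | 0.030-0.046 |
| 0.3 | 0.086 / 0.130 / 0.169 | 0.198 | 0.114-0.186 | 0.038-0.086 |
| 0.5 | 0.110 / 0.194 / 0.272 | 0.270 | 0.186-0.264 | 0.040-0.046 |
| 0.7 | 0.133 / 0.260 / 0.376 | 0.414 | 0.294-0.374 | 0.034-0.062 |

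The simulation error on a true 0.05 is √(0.05 × 0.95/500) ≈ 0.010. A second simulation with visit as a model term (60 or 200 infants, two samples each) gave 9-13%, 15-21% and 24-27% at *r* = 0.2, 0.3 and 0.5.

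**2. Pooled visits, visit left out, composition shifting with age.** The age difference inflates the shuffled variance. If visit explains a share *v* of total variation, the ratio of true to assumed variance becomes (1 + *r*)(1 − *v*), which falls below 1 once *v* > *r*/(1 + *r*). At *r* = 0.3 that point is 0.3/1.3 = 0.23. With *k* = 5 and *r* = 0.3, the level is 0.059 at *v* = 0.2 and 0.014 at *v* = 0.4. Simulated rates were:
- 0.006 (*r* = 0.1, *v* = 0.33)
- 0.028 (*r* = 0.3, *v* = 0.18)
- 0.028 (*r* = 0.5, *v* = 0.21)
- 0.148 (*r* = 0.5, *v* = 0.08)

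The test can therefore err either way.

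**3. Each visit tested alone.** Simulated rates were 0.026-0.084 over all settings, averaging about 0.05. There is no inflation.

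**4. Generalized linear model, effect of the pairing alone.** The ratio of naive to true standard error is 1/√(1 + *r*) for the arm average and 1/√(1 − *r*) for the within-infant change. At *r* = 0.3:
- Arm average: 1/√1.3 = 0.877, so the standard error is 12% too small and P(|Z| > 1.96 × 0.877) = 0.086.
- Change or arm-by-visit: 1/√0.7 = 1.195, so it is 20% too large. A test with 80% power has a standardized effect of 1.96 + 0.84 = 2.80. Its cut-off becomes 1.96 × 1.195 = 2.34, and power falls to Φ(2.80 − 2.34) ≈ 68%.

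Simulated counts (500 infants per arm, mean 5 or 50, log-variance 0.5 or 1.0, *r* = 0.1-0.5, 1500 runs), with over-dispersion allowed for but the pairing ignored, gave 0.052-0.111 for the arm effect.

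**5. Generalized linear model, plain Poisson variance.** In the same simulated data:

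| Variance used | Both visits | One visit |
|---|---|---|
| Plain Poisson | 0.355-0.865 | 0.325-0.842 |
| Infant-clustered (both) / robust (one) | 0.045-0.059 | 0.045-0.064 |

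The one-visit column contains no repeat samples, so most of the error there is over-dispersion. A further simulation on different abundance scales gave 50-69% or 0% for plain Poisson, depending on the scale, and about 4-7% with infant-clustered errors for both the arm and arm-by-visit terms.

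**The case against.** A reader might infer that the SAP treats all 4000 samples as independent and so multiplies false arm differences two- to five-fold. The documents do not support this, for four reasons.

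- **Pooling is not stated.** Section 27 never says that visits are pooled or samples shuffled freely. The singular matrix belongs to the ordination sentence, while the test sentence speaks of matrices. Sections 15 and 26 name two ages, which fits one analysis per visit, and that is valid. The 4000 in the protocol is a laboratory count and does not define an analysis unit.
- **Mixed models are named.** Section 29 does not tie them to the stool data, but it does not exclude that use. They would not repair a permutation test.
- **The multiplier is conditional.** Two- to five-fold fits only pooled permutation at assumed correlations of about 0.2-0.5 with visit accounted for. Over all settings the rate runs from below nominal to about eight-fold (0.414/0.05). For the linear model, pairing alone gives at most about 2.2-fold (0.111/0.05).
- **The stakes are limited.** SAP sections 16 and 17 confine hypothesis testing to the primary outcome and promise secondary results without p-values.

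All four stand as limits on the claim. They do not fill the gap: the SAP still leaves open which test will be run. On the last point, section 27 sets P and Q cut-offs for the microbiota, which conflicts with section 16, so significance statements are foreseeable.

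**Conclusion.** This is an under-specification with real consequences, and it should be closed before analysis. That infants are sampled twice is certain, and the SAP has no rule for it in either the permutation test or the Poisson model.

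- **Permutation test.** If visits are pooled and the pairing ignored, the arm test has a false-positive rate of about 10-27% at assumed correlations of 0.2-0.5 with visit accounted for. Single simulated settings at correlation 0.2 were as low as 6%. With a strong age shift and visit left out, the rate can fall below 5%. If each visit is tested alone, there is no problem.
- **Poisson model.** Ignoring the pairing alone gives about 5-11% for the arm effect and, at correlation 0.3, a standard error about 20% too large for the change and arm-by-visit terms. The larger and less conditional fault is the plain Poisson variance, which misstates the error rate grossly even at one visit.

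The sizes rest on assumed correlations, age shifts and dispersion; the directions do not rest on any one value. The primary result is untouched.

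**What to change.** In SAP section 27:

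- Test arms separately at six weeks and at six months, with one Bray-Curtis matrix per visit. If visits are pooled, put visit in the model and permute arm labels by whole infant, keeping both samples together.
- For genus, resistance-gene and metabolite models that use both visits, include arm, visit and arm-by-visit terms, with standard errors clustered by infant or an infant random effect plus an over-dispersion term.
- Use a robust or over-dispersed variance in any single-visit Poisson model. Clustering by infant alone would not reach that case.
- Define what is meant by a trend.

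In SAP section 29, state which outcomes use the mixed models. Reconcile the significance cut-offs in section 27 with the promise in section 16 to give no p-values for secondary outcomes.

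The cost is SAP wording and a different permutation setting in the software. It needs no new data and loses no samples.
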